#### Section A – Population Distribution

Section A overviews the validity and distribution of women. The analysis is stratified by country, EMT user type, and diagnosis classification whenever reasonable.

Section A-1 Eligibility status (enrollment, exclusions)

Study status of women at follow-up, AT and ITT population

Section A-2 Distribution of women, ITT population

Regional distribution

EMT user type at study entry (starter/switcher/restarter)

Diagnosis classification (endometriosis diagnosis based on surgical procedures or

clinical symptoms)

#### Section B – Population Characteristics

Section B summarizes population characteristics of the participating women derived from baseline and follow-up data. The analysis is stratified by country, EMT user type and diagnosis classification.

Section B-1 Age, height, weight and BMI

Section B-2 Socio-economic characteristics and lifestyle factors

Smoking, education level

Supporting document SOP BMT 01.09 - Doc 5002.02 - Effective date 21.03.2017

Section B-3 Gynecological history

Age at menarche, pregnancies, live births, miscarriages, abortions

and/or stillbirths

Section B-4 Endometriosis characteristics

History of EMT use, time since first diagnosis/ first symptoms, surgical procedures,

endometriosis symptoms

Section B-5 Medical History.

Family history of Anemia, Depression,

History of VTE/ATE

Self-reported history of selected cardiovascular risk factors, treated depression and

diseases, presence of mood symptoms

Section B-6 Medication

Regular use of medication, previous medication

Section B-7 Characteristics of Visanne long-term user, Baseline, and Follow-up

Regional distribution, diagnosis classification, age, BMI, endometriosis symptoms

Section B-8 Follow-up characteristics

Mood symptoms and change to baseline, frequencies and timespan of the first switch

after baseline prescription.

Section B-9 Summary tables of selected baseline characteristics

Frequencies of selected baseline characteristics, additionally shown by age categories

and age-standardized and for women with treatment failure and women who

stopped/switched their treatment

#### Section C - Clinical Outcome

Section C provides incidence rates of primary (Section C1), secondary (Section C2) and safety outcomes (Section C3) and other outcomes of interest (Section C4).

Section C-1 Primary outcomes

The analysis of the primary outcomes (Section C1) is stratified by country, EMT user type and diagnosis classification.

Anemia

Incidence rate of Anemia

Depression

Incidence rate of Depression

Treatment failure

Incidence proportion of treatment failure

Section C-2 Secondary Outcomes

The analysis of the secondary outcomes (Section C2) is stratified by country, EMT user type and diagnosis classification.

Supporting document SOP BMT 01.09 – Doc 5002.02 – Effective date 21.03.2017

#### Treatment discontinuation

Incidence proportion if treatment discontinuation reasons unrelated to treatment

#### failure

#### Depression, Anemia and treatment discontinuation in adolescence

Incidence rates of anemia, depression and incidence proportion of treatment discontinuation in adolescence

#### Depression, Anemia and treatment discontinuation for long-term user

Incidence rates of anemia, depression and incidence proportion of treatment discontinuation in long-term user.

#### Section C-3 Other Safety Outcomes

The analysis of other safety outcomes (Section C3) is stratified by country, EMT user type and diagnosis classification.

#### TE (VTE+ATE)

Incidence rate of confirmed TE (VTE+ATE), TIAs

#### Fatal cases

Incidence rate of all death cases

#### Serious adverse events

Incidence rate of SAEs by organ system (complete cohort and long-term user)

#### Malignant neoplasms

Incidence rate of malignant neoplasms by organ system

#### Malformations of the newborn child

Incidence proportion of all reported deliveries and malformations

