7. FOLLOW-UP

A follow-up assessment for each woman is scheduled 6, 12, 24, 36 and depending on the date of enrollment 48, 60 and 72 months after baseline. Women will be followed-up for at least 3 years. Women recruited in the early phase of the study will be followed-up until study endpoint [max. 6 years].

Follow-up questionnaires will be mailed to the participating women, who often know more about potentially relevant health issues than the physician who made the initial prescription. This is especially true for potential adverse events treated by other physicians. Occasionally, events may be reported by the participant or by a participant's relatives, friends or attending physicians between the regular follow-ups.

These reports will be documented and validated in the same way as regular reports (see section 8).

The follow-up questionnaires will address the occurrence of adverse events. If the woman reports a change in treatment, reasons for switching to another endometriosis treatment or discontinuation of treatment will be requested. In case the regimen was changed or stopped due to a wish to conceive, or due to unintended pregnancy, a follow-up questionnaire requesting data on pregnancy related outcomes (abortions, stillbirths and congenital abnormalities) will be sent to the study participant.

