#### 5.4.5 Definition of other safety outcomes

#### SAEs

SAEs are defined as any adverse event that results in death, a life-threatening experience, inpatient hospitalization, persistent or significant disability/incapacity, or requires medical/surgical intervention to prevent one of the said outcomes. The following items were shown in detail:

- 1. VTE/ATE
- 2. Death
- 3. SAEs by organ system
- 4. Malignant neoplasms
- 5. Malformation of the newborn child

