## 10. Appendix

### I Baseline questionnaire

#### **INAS-VIPOS**

International Active Surveillance Study of Medication Used for the Treatment of Endometriosis:  $\underline{V} is anne \ \underline{P} ost-approval \ \underline{O} bservational \ \underline{S} tudy$ 

	- Baseline Questionnaire -
	Country Physician no. Patient no. ID
If you	have any questions, please call our toll-free number: [telephone number].
	To be filled in by the physician!
1.	What is the name of the medication for endometriosis that you prescribed to your patient today?,
1a.	If you prescribed an oral contraceptive today, have you prescribed an extended regimen? 2
	□ No □ Yes
2.	Please tick the appropriate box to describe today's prescription: 3
	☐ First-time hormonal prescription/no previous hormonal treatment
	☐ Repeat of the same hormonal treatment after a medication break of at least 4 weeks
	☐ Switching from another hormonal treatment without a relevant break (< 4 weeks)
	☐ Switching from another hormonal treatment after a break of at least 4 weeks
3.	How would you classify your patient's endometriosis? 4
	□ Diagnosis based only on clinical symptoms
	☐ Endometriosis confirmed via surgery / laparoscopy
4.	In the last 2 years, how many surgical procedures (diagnostic and/or therapeutical) has your patient received for the management of her endometriosis?
	Number of surgical procedures:
	To be filled in by the study participant!
Pers	onal Data
5.	Please give your date of birth: $\bigcup_{\text{day}}^{\square} \bigcup_{0}^{\square} \bigcup_{\text{month}}^{\square} \bigcup_{\text{year}}^{\square} \bigcup_{\text{year}}^{\square} \bigcup_{0}^{\square} \bigcup_{0}^{\square} \bigcup_{\text{year}}^{\square} \bigcup_{0}^{\square} \bigcup_{0}^{$
6.	What is your height?, cm
7.	What is your weight?kg
Gyn	ecological History
8.	How old were you when you had your first menstrual bleeding?
9.	Have you ever been pregnant? 12
	□ No → go to question 10 □ Yes
9a.	If yes , when did you last give birth? $\frac{DDD}{D}_{12} = \frac{DDD}{D}_{13} = \frac{DDDD}{D}_{14} = DDDDDDDDDDDDDDDDDDDDDDDDDDDDDDDDDDD$
9b.	How many live births have you had?
9c.	How many abortions/miscarriages/still births have you had?
End	ometriosis
10a.	When did you first experience endometriosis symptoms?
10b.	When were you first diagnosed with endometriosis by a physician?    M   M   20   Y   Y   Y   Y   Y   Y   Y   Y   Y

f I

Supporting document SOP BMT 01.09 – Doc 5002.02 – Effective date 21.03.2017

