	Pulmonary embolism 23 ad clot in the deep veins e.g.	3	I was	treated by a physician 26	,	□ Yes	□ No	
	arms or blood clots in the lung)		I was	treated with blood-thinning	drugs 27	□ Yes	□ No	
			If yes	s which drugs?				28
				 				

Supporting document SOP BMT 01.09 – Doc 5002.02 – Effective date 21.03.2017

Dep	ression requiring	□ No	☐ Yes, diagn	osed in	M 30 Y Y Y	31		
treatment 29				eated by a gener	al practitioner 32		Yes	□ No
			l .	eated by a psych Imitted to hospita			∃ Yes ∃ Yes	□ No □ No
			l	ed Suicide 35	11 34		Yes	□ No
Oth	er serious diseases /	□ No	☐ Yes, which					
ope	rations 36		1		37	When?	M M 38 Y	Y . Y . Y J
	gynecological diseases, rtension, diabetes and cancer)		l was	treated by a phy	sician 40		Yes	□ No
			2			When?	MMIY	Y , Y , Y .
			l was	treated by a phy	sician		M_M LY_ month Yes	year □ No
Modi	cations		If you have	had more than 2 seriou	s diseases/operations, p	lease use the	comment field.	
4.	Are you taking any oth	er medica	tion on a requ	lar basis? (NOT	including the med	tication(s)	listed in guestion	1)
-		er medica	don on a regu		one(s)? (please			-
				L 103, Willott	one(s): (picase	aso brain	a name ii knewi	''
	14-1141							42
	oitalization	ماناها هامانده	mr have ver	been admitted	to a boonital (fo	r of loop	t ana niaht) sir	
oa.	With the exception of c [month/year]? 43	iniia aeiive	ery, nave you	been admitted				
	□ No → Go to ques	stion 6		☐ Yes	When	was it?	month 44	year 45
	If yes, was the hosp  ☐ No	oital stay pl	anned? 46	□ Yes				
5b.	What was the reason for	or this hos	pital stay? (PI		ic as possible)			
					. ,			47
50	Was an operation perfo	ormed?						47
36.		Jilleu : 48		□Yes	When	was it?	M M 49	Y . Y . Y I
				L 103	WITCH	was it:	month 49	year 50
	it ves inlease specif	fy the type	of operation:					
Weig	If yes, please specif	fy the type	of operation:					. 51
Weig								
6.	ht	fy the type						51
6. Preg	ht What is your weight?	 	kg					51
6. Preg	ht What is your weight? nancy Have you had a baby s	ince [mon	kg	□ Yes W	hen was the deli	iverv? I	D,D][M,M]	51
6. Preg 7a.	what is your weight?  nancy  Have you had a baby s  □ No → Go to ques	ince [mon	Lighth/year]? 53				day s4 M , M	51 55 Year 56
6. Preg 7a.	what is your weight?  nancy  Have you had a baby s  □ No → Go to ques  Have there been any se	ince [mon	Lighth/year]? 53	problems with t			D_D_S4 M_M_M day 54 month	51 55 year 56

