### Section C-3.6 Incidence proportion of malformations

Table C-3.6.1 Incidence proportion of malformations, AT population, Complete cohort

	DNG		OAED			NAED		Allocation unknown	Total
		GnRH-a	Danazol	All OAED	СНС	Other progestin	All NAED		
Number of deliveries	xx	xx	xx	xx	xx	xx	xx	xx	xx
Malformations	xx	xx	xx	xx	xx	xx	xx	xx	xx
IP** (95% CI)	xx.x (xx.x-x.x)	xx.x (xx.x-x.x)	xx.x (xx.x-x.x)	xx.x (xx.x–x.x)	xx.x (xx.x–x.x)	xx.x (xx.x-x.x)	xx.x (xx.x-x.x)	xx.x (xx.x-x.x)	xx.x (xx.x-x.x)
Thereof last endometriosis treatment exposure									
At conception	xx	xx	xx	xx	XX	xx	XX	xx	xx
	xx.x (xx.x-x.x)	xx.x (xx.x-x.x)	xx.x (xx.x-x.x)	xx.x (xx.x-x.x)					
One cycle before	xx	xx	xx	XX	XX	XX	XX	xx	xx
conception	xx.x (xx.x-x.x)	xx.x (xx.x-x.x)	xx.x (xx.x-x.x)	xx.x (xx.x-x.x)					
More than one cycle	xx	xx	xx	XX	XX	xx	XX	xx	xx
before conception	xx.x (xx.x–x.x)	xx.x (xx.x-x.x)	xx.x (xx.x-x.x)	xx.x (xx.x–x.x)	xx.x (xx.x–x.x)	xx.x (xx.x-x.x)	xx.x (xx.x-x.x)	xx.x (xx.x–x.x)	xx.x (xx.x–x.x)

Note: \* Cohort allocation is based on the intake of the last endometriosis treatment before delivery.

Note: \*\*Incidence proportion is shown per 10^2 deliveries.

Table C-3.6.2	Incidence proportion of malformations, AT population, Starter
Table C-3.6.3	Incidence proportion of malformations, AT population, Switcher
Table C-3.6.4	Incidence proportion of malformations, AT population, Restarter
Table C-3.6.5	Incidence proportion of malformations, AT population, Diagnosis confirmed by surgery
Table C-3.6.6	Incidence proportion of malformations, AT population, Diagnosis based on clinical symptoms
Table C-3.6.7	Incidence proportion of malformations, AT population, Germany
Table C-3.6.8	Incidence proportion of malformations, AT population, Poland
Table C-3.6.9	Incidence proportion of malformations, AT population, Hungary
Table C-3.6.10	Incidence proportion of malformations, AT population, Switzerland
Table C-3.6.11	Incidence proportion of malformations, AT population, Russia
Table C-3.6.12	Incidence proportion of malformations, AT population, Ukraine

Supporting document SOP BMT 01.09 - Doc 5002.02 - Effective date 21.03.2017

Section C-3.7 Other outcomes of interest

Section C-3.8 Incidence rate of surgery / laparoscopy because of endometriosis

Section C-3.1 Incidence rate of surgery / laparoscopy because of endometriosis, ITT population, Complete cohort

	DNG		OAED			NAED		Ex-use	Allocation unknown	Total
		GnRH-a	Danazol	All OAED	СНС	Other progestin	All NAED			

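### The SAP leaves the protocol's pregnancy-outcome data unused: malformations are reported only per delivery, and no table shows follow-up pregnancies by outcome

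*SAP*

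**What the plan says.** Protocol section 7 (Follow-up) covers women whose regimen was changed or stopped for a wish to conceive or an unintended pregnancy. For them, "a follow-up questionnaire requesting data on pregnancy related outcomes (abortions, stillbirths and congenital abnormalities) will be sent to the study participant".

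The SAP takes a narrower line. Section 5.4.5 lists the outcome as "Malformation of the newborn child". Section 8, under Section C-3, plans "Incidence proportion of all reported deliveries and malformations". Mock Table C-3.6.1 opens with "Number of deliveries", expresses malformations per 100 deliveries, and notes that "Cohort allocation is based on the intake of the last endometriosis treatment before delivery". It then splits malformations by whether the last treatment exposure was at conception, one cycle before, or earlier.

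Pregnancy losses are tabulated only as history. The baseline questionnaire asks "How many abortions/miscarriages/still births have you had", and Table B-3.3.1 reports the answers at study entry. The follow-up questionnaire (Appendix II) asks in items 7a and 7b whether the woman has had a baby, the delivery date, and whether the newborn had serious problems. The SAP neither mentions nor reproduces the protocol's pregnancy questionnaire.

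**The concern.** The protocol commits to collecting outcomes for which the SAP has no planned analysis. A malformation proportion restricted to deliveries is conditional on the pregnancy reaching delivery. Whether it does may depend on the malformation itself, for example when a pregnancy is ended after a prenatal finding. Such a pregnancy contributes to neither numerator nor denominator.

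The row for exposure at conception bears most directly on a possible drug effect. A pregnancy conceived on treatment that ends early is also the kind the routine form is least certain to identify. The primary objective includes estimating the absolute risk of rare serious outcomes, so a reader of the final report would expect to see what happened to all known pregnancies.

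**Working it through.** The documents state no malformation rate, hypothesis or sample size, so there is no figure to reproduce. The check is a comparison of texts, followed by a short argument about the direction of bias.

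**1. Collected against analysed**

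| Outcome during follow-up | Route of collection | Planned analysis |
|---|---|---|
| Delivery | Follow-up form, item 7a | Denominator of Table C-3.6.1 |
| Malformation in a newborn | Item 7b; protocol's pregnancy questionnaire | Numerator of Table C-3.6.1; SAE table |
| Stillbirth | Pregnancy questionnaire; possibly item 7a | Table C-3.6.1 only if counted as a delivery (the term is not defined); SAE table if serious |
| Miscarriage or induced abortion | Pregnancy questionnaire; hospital items if admitted | SAE table, only if serious |
| Malformation in a pregnancy ending before delivery | Pregnancy questionnaire | Not in Table C-3.6.1 |

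The SAE tables (C-3.3.1 and, for long-term users, C-3.4.1) report per 10,000 women-years. They give no risk per pregnancy and do not feed Table C-3.6.1.

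**2. The trigger for the pregnancy questionnaire**

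The stop reasons on the follow-up form are trying to become pregnant, treatment duration finished, ineffectiveness, side effects, and a write-in for other reasons. SAP section 5.4.4 lists the reasons unrelated to treatment failure the same way, with no category for unintended pregnancy. A wish to conceive is therefore captured by a box, whereas an unintended pregnancy depends on what the woman writes. A woman who stopped for another reason, later conceived and lost the pregnancy meets neither protocol trigger.

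**3. Direction of bias**

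Let p be the true malformed share of all pregnancies, La the share of affected pregnancies lost before delivery, and Lu the share of unaffected pregnancies lost. The share seen among deliveries is

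p(1 − La) / [p(1 − La) + (1 − p)(1 − Lu)].

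This is below p when La > Lu, equal to p when La = Lu, and above p when La < Lu. None of the three inputs is in the documents, so the values below are assumptions that only show both directions are possible.

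- p = 3%, Lu = 15%, La = 10%: 0.027 / (0.027 + 0.8245) = 3.17%, above the true 3%.
- p = 3%, Lu = 15%, La = 50%: 0.015 / (0.015 + 0.8245) = 1.79%, below it.
- Over p from 2% to 5%, Lu from 10% to 20% and La from 10% to 50%, the seen share runs from about 0.56 to 1.12 times the true share.
- For two cohorts with equal true risk (p = 3%, Lu = 15%), the ratio of seen shares is 1.00 if La is 20% in both, and 0.88 if La is 30% in one and 20% in the other.

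**The case against.** The strongest reply is that the outcome is named for the newborn child, so a delivery denominator matches it. Malformation is also a descriptive other safety outcome, outside the listed primary and secondary objectives. Both statements are correct. They make this an improvement to a safety table and leave the primary analyses untouched. They do not explain why data the protocol plans to collect go unused.

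A reader might infer more than the documents support:

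- **That pregnancy losses are not collected, or that the form cannot identify unintended pregnancies.** Protocol section 7 provides a route for these outcomes. The write-in reason can identify an unintended pregnancy, and mock Table C-2.1.1 breaks such answers into categories, so they are read and classified. Protocol section 8 adds that unclear or missing event information leads to contact with the woman. The questionnaire's absence from the SAP appendices does not show that it is unused.
- **That all losses are absent from the safety report.** Table C-3.3.1 has rows for pregnancy, delivery and puerperium and for malformations, and the follow-up form asks about hospital stays other than for delivery. A loss that meets the seriousness definition has a place; an early loss managed without admission may not.
- **That malformation risk is understated.** This requires affected pregnancies to be lost more often than unaffected ones, which the documents do not establish.
- **That item 7a should be reworded.** Recruitment ended in June 2016 and follow-up ends with QII 2018, so little would be recovered. Two ascertainment regimes would be mixed. Because recruitment was restarted for OAED patients, more of that cohort's follow-up could fall under the new wording.

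**Conclusion.** The point holds as a gap between protocol and SAP. The SAP does not use the planned pregnancy-outcome data, reports malformations only per 100 deliveries, and has no table of follow-up pregnancies by outcome. Affected pregnancies that end before delivery are left out of the malformation proportion, and losses appear only if they qualify as SAEs. Identification of unintended pregnancies is possible but not assured.

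No size can be attached. The bias could run in either direction, and the illustrative values rest entirely on assumed loss rates. The conclusion assumes that the pregnancy questionnaire was used as the protocol describes. If it was not, the report should say so. The change is inexpensive and worth making; no primary hypothesis, power claim or sample size is affected.

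**What to change.** Extend Table C-3.6.1, or add a companion table, to cover all pregnancies reported during follow-up:

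- Name the protocol's pregnancy questionnaire and validated SAE reports as sources.
- Show outcomes as live birth, stillbirth, miscarriage, induced abortion and unknown, by cohort and by exposure at conception.
- Report malformations per pregnancy with known outcome beside the existing per-delivery figure, and state the number of pregnancies with unknown outcome.
- Define delivery, in particular whether a stillbirth counts.
- Replace the allocation rule based on last treatment before delivery with one that also works for pregnancies without a delivery, such as last treatment at or before conception. Item 7a records only the delivery date, so the source of the conception date must be stated.

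The cost is one table and a few lines of SAP text. Separating miscarriage from induced abortion depends on what the pregnancy questionnaire records; the protocol names only abortions, so a combined category may be needed. The main downside is that losses and terminations are reported less completely than births, which is why both denominators should be shown.

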#### Section C-4 Other Outcomes of Interest

The analysis of other outcomes of interest (Section C4) is stratified by country, EMT user type and diagnosis classification.

#### Surgery / laparoscopy because of endometriosis

Incidence rate of all reported surgeries / laparoscopies

#### Self-reported anemia

Incidence rate of self-reported anemia

#### Self-reported depression

Incidence rate of self-reported depression

#### Section D – Comparisons and Inferential Statistics of Primary Outcomes

Section D consists of tables regarding comparisons between main EMT user groups and inferential statistics, i.e. incidence rate ratios (IRR) and multiple regression analysis of primary outcomes (section D1, D2, D3).

Supporting document SOP BMT 01.09 – Doc 5002.02 – Effective date 21.03.2017

#### Section D-1 Anemia

- Incidence Rate Ratio of Anemia between EMT user cohorts (IRR)
- Risk of Anemia measured as HR (Cox model)
   Crude and adjusted HR

#### Section D-2 Depression

- Incidence Rate Ratio of Depression between EMT user cohorts (IRR)
- Risk of Depression measured as HR (Cox model)
   Crude and adjusted HR

#### Section D-3 Treatment Failure

- Incidence Rate Ratio of Treatment Failure between EMT user cohorts (IRR)
- Risk of Treatment Failure measured as HR (Cox model)
   Crude and adjusted HR

Supporting document SOP BMT 01.09 – Doc 5002.02 – Effective date 21.03.2017

## 10. Appendix

### I Baseline questionnaire

#### **INAS-VIPOS**

International Active Surveillance Study of Medication Used for the Treatment of Endometriosis:  $\underline{V} is anne \ \underline{P} ost-approval \ \underline{O} bservational \ \underline{S} tudy$ 

	- Baseline Questionnaire -
	Country Physician no. Patient no. ID
If you	have any questions, please call our toll-free number: [telephone number].
	To be filled in by the physician!
1.	What is the name of the medication for endometriosis that you prescribed to your patient today?,
1a.	If you prescribed an oral contraceptive today, have you prescribed an extended regimen? 2
	□ No □ Yes
2.	Please tick the appropriate box to describe today's prescription: 3
	☐ First-time hormonal prescription/no previous hormonal treatment
	☐ Repeat of the same hormonal treatment after a medication break of at least 4 weeks
	☐ Switching from another hormonal treatment without a relevant break (< 4 weeks)
	☐ Switching from another hormonal treatment after a break of at least 4 weeks
3.	How would you classify your patient's endometriosis? 4
	□ Diagnosis based only on clinical symptoms
	☐ Endometriosis confirmed via surgery / laparoscopy
4.	In the last 2 years, how many surgical procedures (diagnostic and/or therapeutical) has your patient received for the management of her endometriosis?
	Number of surgical procedures:
	To be filled in by the study participant!
Pers	onal Data
5.	Please give your date of birth: $\bigcup_{\text{day}}^{\square} \bigcup_{0}^{\square} \bigcup_{\text{month}}^{\square} \bigcup_{\text{year}}^{\square} \bigcup_{\text{year}}^{\square} \bigcup_{0}^{\square} \bigcup_{0}^{\square} \bigcup_{\text{year}}^{\square} \bigcup_{0}^{\square} \bigcup_{0}^{$
6.	What is your height?, cm
7.	What is your weight?kg
Gyn	ecological History
8.	How old were you when you had your first menstrual bleeding?
9.	Have you ever been pregnant? 12
	□ No → go to question 10 □ Yes
9a.	If yes , when did you last give birth? $\frac{DDD}{D}_{12} = \frac{DDD}{D}_{13} = \frac{DDDD}{D}_{14} = DDDDDDDDDDDDDDDDDDDDDDDDDDDDDDDDDDD$
9b.	How many live births have you had?
9c.	How many abortions/miscarriages/still births have you had?
End	ometriosis
10a.	When did you first experience endometriosis symptoms?
10b.	When were you first diagnosed with endometriosis by a physician?    M   M   20   Y   Y   Y   Y   Y   Y   Y   Y   Y

f I

Supporting document SOP BMT 01.09 – Doc 5002.02 – Effective date 21.03.2017

11.	What symptoms do you have associated wit	th your end	ometriosis	? (plea	ase tick all that apply)	
	$\Box$ Pelvic pain unrelated to period pain $_{\rm 22}$		□ Pain v	vhen pa	assing urine 27	
	☐ Experienced pain during or after sexual inter	course 23	☐ Pain d	luring b	owel movement 28	
	☐ Difficulty conceiving/infertility 24		☐ Const	ipation	or diarrhoea 29	
	☐ Painful periods 25		☐ Tiredn	iess / V	Veakness 30	
	$\square$ Heavy or irregular bleeding $_{26}$		☐ Other;	which	31 32	
12.	Have you had disabling pain associated with events on least two days in the last 4 weeks		metriosis	preve	nting you from working or attending social	
	□ No □ Yes					
13.	Please rate the pain associated with your er last 4 weeks, with 0 being no pain and 10 be				box that best describes your pain over the	
	no pain 0 1 2 3 4 5	6	7	9	unbearable pain	
14.	Have you had an operation to diagnose and		ur endome	triosis	? 35	
	□ No → go on to question 15	☐ Yes				
	If yes, please list the operation (if known) and t removal of ovarian cyst, hysterectomy, colonos For additional space, use comment section on page 4.					
	Operation 36				Date	
					M M J 37 Y Y Y Y 38	
					M M Y Y Y Y	
					M M Y Y Y Y Y	
					M M Y Y Y Y Y	
15.	Before today's prescription, have you been	prescribed	any other	medic		
	□ No → go on to question 16	☐ Yes				
	If yes , please list all the prescribed medication contraceptive, IUD, progestine, GnRH). Also give section on page 4.					
Na	me (type) of medication 40		from		to	
		M M 41	Y Y Y	Y J 42	M M 43 Y Y Y Y Y 44 □ ongoing 45	
		M M month	Y Y Y year	Y	M,M, Y,Y,Y,Y ☐ ongoing	
		M M L	Y Y Y	Υ	M,M (Y, Y, Y, Y) ☐ ongoing	
		M M L	Y Y Y Y	Υ	M M Y Y Y Y Y ☐ ongoing	
Med	lication					
16.	Are you taking any other medication on a re	gular basis	? (EXCLU	DING t	oday's prescription) 48	
	□ No □ Yes, which one(s)? (please use Trade Name if known)					
					47	
17.	Beyond today's prescribed medication, wha	t are you cu	irrently do	ing to	alleviate your endometriosis symptoms?	
	$\square$ Non-prescription pain killers $_{^{48}}$		Massage/	manual	therapy 52	
	☐ Natural/herbal products ₄9		Home rem	nedies (	(eg. hot water bottle) 53	
	☐ Acupuncture 50		Nothing el	se 54		
	☐ Dietary modification ₅1		Other; ple	ase spe	ecify 55 56	

2

Supporting document SOP BMT 01.09 – Doc 5002.02 – Effective date 21.03.2017

Medical History  18. Have you ever been told	by a physic	an that you had or have any of the following diseases or conditions? Please
		condition was treated by a physician.
Deep venous thrombosis 57 (blood clot in the deep veins e.g. legs/arms)	□ No	☐ Yes, in MMM Self Y Y Y Y Y Self Self Self Self Self Self Self Self
logarams/		I was treated by a physician 60 □ Yes □ No
		I was treated with blood-thinning drugs ₅₁ ☐ Yes ☐ No
Pulmonary embolism 62 (blood clot in the lung)	□ No	Yes, in  M, M, Y, Y, Y, Y,  month 63 year 64
		I was treated by a physician ⊕5 ☐ Yes ☐ No
		I was treated with blood-thinning drugs ₅ □ Yes □ No
Myocardial infarction 67 (heart attack)	□ No	Yes, in
		I was treated by a physician 70 ☐ Yes ☐ No
		If yes, was an ECG performed? ₁₁ ☐ Yes ☐ No
		Was the infarction confirmed by an ECG? ₁₂ ☐ Yes ☐ No
Stroke 73	□ No	Yes, in  M M 74 Y Y Y Y 75
		I was treated by a physician 76 ☐ Yes ☐ No
Anemia 77	□ No	Yes, diagnosed in worth 78 year 79
		I was treated by a physician 80 □ Yes □ No
		I received a blood or iron trans-/infusion 81 ☐ Yes ☐ No
		I took iron tablets 82 ☐ Yes ☐ No
Depression requiring treatment 83	□ No	☐ Yes, diagnosed in [M N set Y Y Y Y Y Y Set Y year Y Set Y year Y Set Y Y Y Y Y Y Set Y Y Y Y Y Y Y Y Y Y Y Y Y Y Y Y Y Y Y
		I was treated by a general practitioner 86 ☐ Yes ☐ No
		I was treated by a psychiatrist 87 ☐ Yes ☐ No
		I was admitted to hospital 88 ☐ Yes ☐ No
		There was a suicide attempt № □ Yes □ No
Cancer 90 (e.g. Breast cancer)	□No	☐ Yes, diagnosed in [M, M] [Y, Y, Y, Y] [92] year
		What kind of cancer?
		I was treated by a physician 94 ☐ Yes ☐ No
Other serious diseases 95 (e.g. hypertension, diabetes, benign	□ No	☐ Yes, which?
tumor)		1
		I was treated by a physician ₅ □ Yes □ No
		2 When? M.M. Y.Y.Y.Y.Y.
		I was treated by a physician ☐ Yes ☐ No
		If you have had more than 2 serious diseases, please use the space in the comment section on page 4.
Operations 100	□ No	☐ Yes, I had operation(s), which?
(excluding those listed in Q14)		1
		2 When?
		If you have had more than 2 operations, please use the space in the comment section on page 4.

3

Supporting document SOP BMT 01.09 – Doc 5002.02 – Effective date 21.03.2017

Relat	tives				
19.	-	or sister(s) been diagnosed	d with endometriosis?		
	□ None 104	☐ Mother 105	☐ Sister	. ,	
20.		parent(s) or sibling(s) beer			1 P
	□ None 107	☐ Mother 108	☐ Fathe		bling(s) 110
21.	(blood clot in the I	•	•	, ,	
Mood	□ None 111	☐ Mother 112	☐ Fathe	r 113	bling(s) 114
	We are interested	in finding out about the in changes over the course one of the course of			
22a	ı. Have you been fe	eling down, depressed or l	hopeless? 115		
	☐ Never	☐ Rarely	□ Sometimes	☐ Often	☐ Always
22b	. Have you been fe	eling like you are a failure	and have let down your	friends and/or family	? 116
	□ Never	□ Rarely	□ Sometimes	☐ Often	☐ Always
220	. Have you felt hap	py or optimistic about the	future? 117		
	□ Never	□ Rarely	□ Sometimes	☐ Often	☐ Always
Lifes	tyle				
23.	Do you regularly s	smoke cigarettes (at least	one cigarette a day)? 118		
	□ Yes	On average	e, how many cigarettes p	er day?	Cigarettes
	□ No, stopped sm	oking On average smoke in the	e, how many cigarettes a ne past?	day did you	Cigarettes
	☐ No, never smok	ed regularly	•	119	· ·
Educ	ation				
24.	What is your mos	t advanced school or colle	ege degree? 120		
	☐ No school-lea	aving certificate			
	☐ High school of	diploma			
	☐ Community of	ollege			
	☐ University / te	echnical college			
	Please fill in to	day's date:	21 month 122 year 123		
	nment				
Ple	ase tell us anything	g else you'd like us to know	W : 124		

Thanks a lot for your help!

Supporting document SOP BMT 01.09 – Doc 5002.02 – Effective date 21.03.2017

